2.3 Patient disposition, demographics and other baseline characteristics

2.3.1 Patient disposition

The FAS and ENR will be used to prepare a summary of patient disposition. The FAS will be used to prepare a patient disposition listing.

The number and percentage of subjects who completed the study and discontinued from the study will be summarized by treatment with reasons for premature discontinuation. In addition, the number of screen failures with reasons will be presented for all screened subjects. Patient identification number and whether subjects completed or discontinued from the study will be listed, with date of last dose and primary reason for premature discontinuation.

2.3.2 Protocol deviation

The number and percentage of subjects with protocol deviations will be tabulated by category and deviation for the FAS. Separate summary for protocol deviation due to COVID - 19 will be provided for FAS. Subjects with protocol deviations will be listed with date and study day of occurrence, deviation and severity codes.

The number of subjects included in each analysis set will be tabulated for FAS Reasons for exclusion from analysis sets will be tabulated for the FAS. Patient exclusion from analysis sets will be listed for all subjects with reasons for exclusion (i.e., both protocol and non-protocol deviations).

2.3.3 Demographic characteristics

Demographic and Baseline characteristics will be listed and summarized descriptively by treatment group and total for the FAS and the safety set.

The following demographic and vital signs variables collected in the eCRF at Baseline will be summarized:

- Sex (Male, Female)
- Age (in years)
- Age category (≥ 18 - ≤ 64 , > 64 - ≤ 75 , > 75)
- Country (Germany, Other)
- Race (Caucasian, Black, Asian, Other)
- Height (cm)
- Weight (kg)
- Body mass index (BMI) (kg/m²)
- BMI (< 25 kg/m², 25 - < 30 kg/m² and ≥ 30.0 kg/m²)
- Vital signs (sitting systolic/diastolic blood pressure (mmHg), sitting pulse rate (bpm))
- Smoking status (never, current, former)

The following Baseline disease characteristics will be summarized:

- Diagnosis of axSpA (Yes, No)
- Classification of axSpA (r-axSpA, nr-axSpA)
- Time since first signs and symptoms of axSpA (years)
- Inflammatory back pain: (Yes, No)
- Time since onset of inflammatory back pain until ax-SpA diagnosis (years)
- Arthritis: (Yes, No)
- Uveitis: (Yes, No)
- Dactylitis: (Yes, No)
- Enthesitis (Yes, No)
- Psoriasis: (Yes, No)
- Crohn's disease or colitis: (Yes, No)
- [REDACTED]
- Good response to NSAIDs: (Yes, No)
- Family history for SpA: (Yes, No)
- HLA-B27 positive: (Yes, No)
- Elevated CRP: (Yes, No)
- [REDACTED]
- Radiographic evidence for sacroiliitis according to the mNY criteria : (Yes, No)
- ASDAS-CRP
- ASDAS- ESR
- ESR
- CRP
- C-Reactive Protein (mg/L) (≤ 5 , > 5)
- Quick CRP
- Quick C-Reactive Protein(mg/L) (≤ 5 , > 5)
- [REDACTED]
- [REDACTED]
- [REDACTED]
- Back pain (BASDAI)
- Overall Level Fatigue/Tiredness (BASDAI question 1)

- Overall Neck, Back, Hip Pain (BASDAI question 2)
- Pain Joint O/T Neck, Back, Hip (BASDAI question 3)
- Discomfort Tender Area to Touch (BASDAI question 4)
- Overall Level Morning Stiffness (BASDAI question 5)
- Morning Stiffness From Wakeup (BASDAI question 6)
- Patient/physician global assessment
- ASAS-HI
- BASFI
- BASMI
- Chest expansion
- SF- 36
- FACIT- fatigue

Time since (in years) of symptoms is calculated as (start date of treatment – date of first diagnosis of symptom + 1)/365.25.

2.3.4 Relevant medical history/ current medical condition

Medical history/ current medical conditions will be coded using the Medical Dictionary for Regulatory Activities (MedDRA) terminology. History/conditions will be summarized for the FAS by primary system organ class, preferred term (PT), treatment group and overall. Verbatim recorded history/conditions will be listed together with the coded terms, date of diagnosis/surgery and whether the problem was ongoing at start of the study.

2.3.4.1 Cardiovascular risk factors

Number and percentage of subjects with specific cardiovascular risk factors will be summarized. In addition, the number and percentage of subjects with 0, 1, 2, 3, 4 or more cardiovascular risk factors will be summarized. Cardiovascular risk factors are defined as the following medical histories/conditions:

- CCV history/condition
- Hypertension
- Lipidemia (dyslipidemia/hyperlipidemia)
- Diabetes (complicated/uncomplicated)
- Prior transient ischemic attack
- Prior hemorrhagic stroke
- Prior ischemic stroke
- Prior stroke (unknown type)
- Myocardial infarction
- Atrial fibrillation

- Supraventricular
- Tachycardia
- Deep vein thrombosis
- Pulmonary embolism

2.4 Treatments (study treatment, rescue medication, concomitant therapies)

2.4.1 Study treatment

Duration of exposure

The number of injections will be summarized by treatment groups, overall and within treatment periods. Duration of exposure to the study treatment will be calculated as the number of days between the first dose date and the last dose date exposed to that treatment over the specified period (expressed as: Duration of exposure = Date of last known dose of study drug – Date of first dose of study drug + 1).

The duration of exposure (in days) to the study treatment by treatment group (T2T, SOC, Other and Overall) will be summarized for the safety set as below

- a continuous variable with the standard descriptive statistics, and
- a categorical variable classified into < 12 weeks, ≥ 12 and < 24 weeks, ≥ 24 and < 36 weeks, ≥ 36 weeks with number and percentage of subjects in each category.
- On-treatment exposure = Date of last known dose of study drug – Date of first dose of study drug + 1 + 30).

Furthermore, the T2T arm will be summarized by treatment (secukinumab 150 mg, secukinumab 300 mg, adalimumab 40 mg). The T2T arm will also be summarized for actual treatment arm.

Similarly, in the SOC arm all medications will be summarized along with their drug class.

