6.1.3 Treatment duration

Each patient will be treated for a maximum of 36 weeks (last dose of secukinumab at Week 32, last dose of adalimumab biosimilar (Hyrimoz®) at Week 34).

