- Achieves ASDAS clinically important improvement (i.e. responder) will continue with secukinumab 300 mg s.c. every 4 weeks up to Week 32.
- Do not achieve ASDAS clinically important improvement (i.e. non-responder), will be switched to adalimumab biosimilar (GP2017) 40 mg s.c. every 2 weeks until Week 34.

Escape arm

- Subjects who are receiving 150 mg secukinumab (i.e. were responders at Week 12) can be escalated at Week 24 to 300 mg secukinumab every 4 weeks until Week 32 if they experience a loss of response, where loss of response is defined as ASDAS change from Baseline <1.1 .

If the ASDAS measurement is missing at a visit, it is assumed that the planned dose continues for the next treatment period.

Standard of Care Regimen

Patients will receive treatment according to local practice standards by their treating physician following the current treatment recommendations with NSAIDs as the first-choice drug treatment and disease-modifying anti-rheumatic drugs (DMARDs) for patients with active disease because of a lack of response, intolerance, or contraindication to NSAIDs ([van der Heijde et al 2017](#)). Patients will be seen every 12 weeks or more often, if clinically indicated up to Week 36; assessment of the outcome parameters will be performed at Week 12, Week 24 and Week 36.

Study treatment (T2T) start and end date: Study treatment start date is defined as the first date of study drug administration and recorded on the Drug Administration Record (DAR) Electronic Case Report Form (eCRF) page. Similarly, study drug end date is defined as the last date of study drug administration and is recorded on the DAR eCRF page.

SOC treatment start and end date: SOC treatment start date is defined as the first date of any SOC drug for AxSPA treatment after randomization. Similarly, SOC drug end date is inferred as the last date of any SOC drug administration for AxSPA treatment within the treatment phase.

Study day: Study Day 1 is defined as the first day of administration of randomized study treatment. Study day will be calculated as (event date – study drug start date + 1 day) for events that occurred on or after study drug start date (e.g. visit, lab samples, AEs). For events prior to study drug start date (e.g. time since diagnosis), study day will be negative and calculated as (event date – study drug start date).

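### SAP 2.4.1 counts exposure only to the last injection, so a T2T course given as planned is tabulated as under 36 weeks and the by-drug table loses the interval after each drug's last dose

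*SAP*

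**What the plan says.** SAP 2.4.1 defines duration of exposure as "the number of days between the first dose date and the last dose date" and gives the formula "Duration of exposure = Date of last known dose of study drug – Date of first dose of study drug + 1". The list that follows summarises this duration as a continuous variable and in classes, the highest being "≥ 24 and < 36 weeks, ≥ 36 weeks with number and percentage of subjects in each category". The T2T arm is also to be summarised separately for secukinumab 150 mg, secukinumab 300 mg and adalimumab.

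The same list contains a second measure, "On-treatment exposure = Date of last known dose of study drug – Date of first dose of study drug + 1 + 30". The SAP does not say that the classes apply to it.

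Protocol 6.1.3 states "Each patient will be treated for a maximum of 36 weeks" and in the same sentence puts the "last dose of secukinumab at Week 32". For patients switched at Week 24, SAP 2.1.1 gives "adalimumab biosimilar (GP2017) 40 mg s.c. every 2 weeks until Week 34". The protocol thus treats the interval after the final injection as part of the 36 weeks.

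For the comparator, SAP 2.1.1 says "SOC drug end date is inferred as the last date of any SOC drug administration for AxSPA treatment within the treatment phase". The treatment phase normally ends the day before the Week 36 visit. If the documented end of treatment is on or after that visit, the phase ends on that date.

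**The concern.** With drugs injected every 4 or every 2 weeks, stopping the clock on the day of the last injection leaves out the interval which that injection is meant to cover. This has two consequences.

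- In the categorical table, T2T patients who received every planned dose sit in the class below 36 weeks. SOC patients on a daily tablet can sit in the class above, although both were treated for the same calendar time.
- In the by-drug table, the interval is lost after each drug's last dose, including the gap before each escalation or switch. Time on each T2T drug is understated, and the by-drug days do not add up to the arm-level days for the same patient.

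What is at stake is whether the exposure tables describe correctly how long patients were treated.

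**Working it through.** **Inputs.** Dosing weeks are from Protocol Table 8-2, visit tolerances from Protocol 6.6.1 (Visits 10 to 15: ±7 days on secukinumab, ±3 days on adalimumab), and the formula and classes from SAP 2.4.1. The treatment phase is from SAP 2.1.1.

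**Calendar check.** Scheduled day = 7 × week + 1 gives Day 85, 169 and 253 for Weeks 12, 24 and 36, as in SAP Table 2-1. The top class starts at 36 × 7 = 252 days.

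**Arm level, T2T (last day − first day + 1, first dose on Day 1).**

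| Course | Last dose | Duration | Share of 252 | Latest within tolerance |
|---|---|---|---|---|
| Ends on secukinumab | Week 32, Day 225 | 225 days (32.1 weeks) | 89% | 225 + 7 = 232 |
| Ends on adalimumab | Week 34, Day 239 | 239 days (34.1 weeks) | 95% | 239 + 3 = 242 |

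The shortfalls are 27 and 13 days (11% and 5%). Even at the latest permitted day, 20 and 10 days are missing.

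**Arm level, SOC, daily drug.**

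- Start on Day 1, Week 36 visit on Day 253: the phase ends on Day 252, giving 252 days, which is in the top class.
- Start on Day 1, visit one day early (Day 252): 251 days, or 252 if end of treatment is dated on the visit day.
- Start on Day 2, visit on Day 253: 251 days, or 252 if end of treatment is dated on the visit day.

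**By drug, T2T patient taking all three steps.**

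- Secukinumab 150 mg, Weeks 0 to 8: Days 1 to 57 = 57 days.
- Secukinumab 300 mg, Weeks 12 to 20: Days 85 to 141 = 57 days.
- Adalimumab, Weeks 24 to 34: Days 169 to 239 = 71 days.
- Sum: 185 of 252 days (73%), against 239 at arm level for the same patient.

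A patient with one change, from 150 mg to 300 mg at Week 12, gets 57 + (225 − 85 + 1) = 57 + 141 = 198 of 252 days (79%).

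**The +30 measure.** At arm level it gives 225 + 30 = 255 and 239 + 30 = 269 days. By drug, the three-step patient gets 87 + 87 + 101 = 275 days, more than the 252 planned. A daily SOC drug would get 252 + 30 = 282, so the 27-day gap to a secukinumab course remains (282 − 255).

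**Counting to the day before the next dose was due.**

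- Arm level: 225 + 27 = 252 (secukinumab) and 239 + 13 = 252 (adalimumab).
- By drug, three steps: Days 1–84, 85–168 and 169–252, so 84 + 84 + 84 = 252.
- Week 36 visit 7 days early (Day 246): the phase ends on Day 245, giving 245 days = 35.0 weeks.

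**The case against.** The strongest reply is that little depends on this variable. Adverse events are planned as counts and as numbers and percentages of subjects (Protocol 12.5.2, SAP 2.8.1), and the on-treatment window has its own definition in SAP 2.1.1. A reader might infer that exposure is the denominator of the safety results and that these are therefore distorted. The documents do not support that, because no exposure-adjusted rate is specified.

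Further points stand in part:

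- **The SAP also lists a +30-day measure.** It does, and a full course exceeds 252 days on it. But it is not tied to the classes, and by drug it over-counts.
- **A completed course is visible elsewhere.** Injection counts (SAP 2.4.1), compliance (Protocol 12.3) and disposition (SAP 2.3.1) would show it. That softens the consequence but does not correct the exposure table.
- **The arms share one formula.** True. SOC may include injected biologics, which lose their last interval in the same way, and SOC starts at the first drug after randomization. The contrast holds only for SOC patients on daily drugs, and then narrowly.
- **The 73% figure is the extreme.** It applies only to the by-drug split for patients who go through all three steps. A reader might take 27% as the general understatement; at arm level it is 5–11%.
- **The top class is not strictly unreachable in T2T.** A last dose at least 27 days late (secukinumab) or 13 days late (adalimumab), or a missing end date replaced by the end-of-treatment date (SAP 5.1.1), could reach 252 days.

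**Conclusion.** The point holds for the variable that the SAP categorises. Every T2T patient fully treated on schedule or within the protocol tolerances, with recorded dose dates, is classed as at least 24 but under 36 weeks. The protocol describes the same course as 36 weeks. The shortfall is 13 to 27 days per patient at arm level. By drug, it rises to 67 of 252 days for a patient taking all three steps (252 − 185).

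The effect is confined to descriptive exposure tables in the Safety Set. Adverse event counts and percentages and all efficacy analyses are unchanged. The figures assume a first dose on Day 1 and the dosing weeks of Protocol Table 8-2.

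**What to change.** Replace the derivation in SAP 2.4.1. Exposure to each T2T drug should end at the earliest of:

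1. the day before the next dose would have been due under the protocol's own schedule: 7 days after a loading dose that is followed by another weekly dose, 28 days after a secukinumab dose that starts a 4-week interval, 14 days after an adalimumab dose;
2. the day before the next T2T drug starts;
3. the end of the treatment phase.

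Taking the interval actually due matters for early stops. A patient whose last dose is at Week 1 (Day 8) is credited with 14 days; a flat 28-day rule would credit 35.

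Use the same last-dose-plus-interval rule for injected biologics in the SOC arm, with their recorded dosing interval, so that the imbalance is not simply reversed. Use the variable for the arm-level, by-drug and categorical summaries, and state that the classes refer to it and not to the +30 measure.

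Set the top class to allow for the visit window, for example at least 35 weeks (245 days). Otherwise a fully treated patient whose Week 36 visit is up to 7 days early would still miss it.

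The cost is slightly more derivation work, including the interval for SOC injectables. Protocol 6.6.1 already requires administration dates to be recorded in both arms. No dose, visit or test changes.

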2.4.2 Prior, concomitant and non-drug therapies/procedures

Each medication has the start and end dates recorded on the eCRF. Prior medications are defined as those medications which were taken and stopped prior to first dose of study treatment. Concomitant medications are defined as any medication given at least once between the day of first dose of randomized study treatment and the last day of study visit, including those which were started pre-Baseline and continued into the treatment period. The below summary tables will be reported for:

- a. Prior medication
- b. Concomitant medications which started prior or on/after the first dose of study treatment but before end of the treatment phase.
- c. Follow-up medications which started after the treatment phase

Rescue medications will be summarized separately by treatment group.

All prior and concomitant medications will be coded using the latest version of the WHO drug dictionary. All concomitant medications will be listed and summarized in alphabetical order according to the Anatomical Therapeutic Chemical (ATC) classification system and PT by treatment group. Tables will also show the overall number and percentage of subjects receiving at least one treatment of a particular ATC. Non drug therapies and procedures will be listed according to collected term in alphabetical order.

Categories of concomitant medications are outlined in [Appendix 5.3](#).

For handling of missing or incomplete start and end dates, see [Appendix 5.1.3](#) of this document.

All summaries will be on the safety set.

2.5 Analysis of the primary objective

The primary objective of the study is to demonstrate an advantage of an intensified T2T (secukinumab) approach, as measured by the proportion of subjects achieving ASAS40 response, when compared to a SOC treatment regimen in subjects with active axSpA inadequately responding to NSAID therapy.

2.5.1 Primary endpoint

The primary endpoint variable is the proportion of subjects achieving treatment response as defined by the ASAS40 criteria at Week 24.

ASAS responder: ASAS responder will be derived based on the following ASAS domains:

1. Patient's global assessment of disease activity measured on a VAS scale.
2. Patient's assessment of back pain, represented by either total or nocturnal pain scores, both measured on a VAS scale.
3. Function represented by BASFI average of 10 questions regarding ability to perform specific tasks as measured by VAS scale.
4. Inflammation represented by mean duration and severity of morning stiffness, represented by the average of the last 2 questions on the 6-question BASDAI as measured by a VAS scale.

Additional assessment domains:

5. Spinal mobility represented by the BASMI lateral spinal flexion assessment.
6. CRP (acute phase reactant).

ASAS response criteria 40% (ASAS 40): ASAS40 response is defined as an improvement of $\geq 40\%$ and ≥ 2 units on a scale of 10 in at least 3 of the 4 domains and no worsening at all in the remaining domain.

ASAS response criteria 20% (ASAS 20): ASAS20 response is defined as an improvement of $\geq 20\%$ and ≥ 1 unit on a scale of 0 to 10 in at least 3 of the 4 domains, and no worsening of $\geq 20\%$ and ≥ 1 unit at all in the remaining domain.

ASAS partial remission (PR): ASAS partial response is defined as a score of < 2 units on a scale of 10 for all 4 core ASAS domains.

2.5.2 Statistical hypothesis, model, and method of analysis

The null hypothesis to be rejected is that the odds of ASAS40 response at Week 24 are equal in both treatment groups. The corresponding alternative hypothesis is that the odds of response at Week 24 are higher under the secukinumab T2T approach compared to a SOC regimen.

Let p_j denote the proportion of ASAS40 responders at 24 weeks for treatment group j , $j=0,1$ where

0 corresponds to the SOC regimen

1 corresponds to the secukinumab T2T regimen

The following hypotheses will be tested:

$H_0: (p_1 / 1-p_1) / (p_0 / 1-p_0) = 1$ vs. $H_A: (p_1 / 1-p_1) / (p_0 / 1-p_0) \neq 1$

In other words:

H_A : The odds ratio (OR) of achieving an ASAS40 response at Week 24 for the comparison of secukinumab T2T vs. SOC is different from 1.

The **primary analysis** will be performed comparing treatments with respect to the primary efficacy variable in a multiple logistic regression model with treatment and center as factors and weight as well as Baseline CRP level as covariates. The adjusted OR, the corresponding 95% confidence interval (CI) and the p-value will be given. The H_0 of equal odds will be rejected if the 2-sided p-value from the logistic regression model for the factor “treatment” is < 0.05 ; however, superiority of secukinumab T2T approach will be claimed only if the direction is correct, i.e. if the odds of response are larger under secukinumab T2T approach.

Tables will also show the number and percentage of patients achieving ASAS40 response.

The primary efficacy analysis will be based on the FAS. The primary analysis will be performed when all subjects have completed the Week 24 assessment.

2.5.3 Handling of missing values/censoring/discontinuations

Subjects will be analyzed irrespective of adherence to assigned treatment regimen. Subjects without a valid ASAS40 assessment at Week 24 will be regarded as non-responders for the primary analysis.

In case of substantial missing data in the primary analysis, alternative approaches will be assessed by repeating the logistic regression model using ways to handle missing values. These may include, but are not limited to:

- Multiple imputation
- Observed data analysis

2.5.4 Supportive analyses

Supportive analyses will be conducted in order to provide evidence that the results seen from the primary model are robust. Possible effect modification due to patient characteristics will be explored by subgroup analyses for sex (male, female), age class (≥ 18 to ≤ 64 , > 64 to ≤ 75 , > 75 years), disease severity based on ASDAS (< 1.3 , ≥ 1.3 to < 2.1 , ≥ 2.1) and CRP blood level

(≤ 5, > 5) (mg/L) at Baseline. The primary model may also be recalculated with these factors included as well as with the respective terms for a subgroup by treatment interaction.

2.6 Analysis of the key secondary objective

There are no key secondary objectives in this study.

2.7 Analysis of secondary [REDACTED] efficacy objective(s)

2.7.1 Secondary [REDACTED] endpoints

Secondary efficacy [REDACTED] assessments will be evaluated based on the FAS and listed by treatment and visit on the FAS.

The following secondary efficacy [REDACTED] endpoints will be evaluated applying methods as defined below:

Table 2-2 Secondary [REDACTED] variables

Secondary [REDACTED] endpoint	Time point	Model/Method
ASAS40 response	Week 12 [REDACTED]	Multiple logistic regression
ASAS20 response	Week 12, Week 24 [REDACTED]	Multiple logistic regression
ASAS PR	Week 12, Week 24 [REDACTED]	Multiple logistic regression
AS disease activity score • ASDAS clinically important improvement (defined as change from BSL of ≥1.1) • ASDAS major improvement (defined as change from BSL ≥ 2.0) • ASDAS<1.3 • ASDAS<2.1 (low disease activity)	Week 12, Week 24 [REDACTED]	Multiple logistic regression
BASDAI 50	Week 12, Week 24 [REDACTED]	Multiple logistic regression

Secondary [REDACTED] endpoint	Time point	Model/Method
Improvement of disease activity, function, axial mobility, and quality of life measures compared to Baseline according to:		
BASDAI change from Baseline	Week 12, Week 24 [REDACTED]	MMRM
ASDAS change from Baseline	Week 12, Week 24 [REDACTED]	MMRM
Change from Baseline in CRP and ESR	Week 12, Week 24 [REDACTED]	MMRM
Change from Baseline in BASFI	Week 12, Week 24 [REDACTED]	MMRM
Change from Baseline in BASMI	Week 12, Week 24 [REDACTED]	MMRM
Change from Baseline in chest expansion	Week 12, Week 24 [REDACTED]	MMRM
Change from Baseline in Patient's Global assessment of disease activity	Week 12, Week 24 [REDACTED]	MMRM
Change from Baseline in Physician's Global assessment (VAS scale) of disease activity	Week 12, Week 24 [REDACTED]	MMRM
Change from Baseline in ASAS- HI	Week 12, Week 24 [REDACTED]	MMRM
Change from Baseline in SF-36 domain scores	Week 12, Week 24 [REDACTED]	MMRM
Change from Baseline in SF-36 PCS and MCS	Week 12, Week 24 [REDACTED]	MMRM
SF-36 Response	Week 12, Week 24 [REDACTED]	Multiple logistic regression
Change from Baseline in ASQoL	Week 12, Week 24 [REDACTED]	MMRM
Change from Baseline in FACIT-Fatigue	Week 12, Week 24 [REDACTED]	MMRM

Secondary endpoint	Time point	Model/Method

